	B Demographic and Other Baseline Variables	
	Disposition of Subjects	
	Efficacy Analysis	
	Treatment by Center Interaction	
17.9.7	⁷ Safety Analysis	74
17.9.8	Handling of Missing Data	74
18.	DATA MONITORING PLAN	75
19.	DATA CONFIDENTIALITY	76
20.	FUNDING	77
21.	ETHICS	77
22.	INFORMED CONSENT	78
23.	REGULATORY AND HEALTH AUTHORITY AUDITS	79
24.	ELECTRONIC REPORTING OF DATA	79
25.	RECORD RETENTION	80
26.	PROTOCOL MODIFICATIONS	80
27.	PUBLICATION POLICY	80
28.	SUBJECT / STUDY DISCONTINUATION	80
29.	DEVICE ACCOUNTABILITY	82
30.	APPENDICES	83
31.	REFERENCES	83

Doc No: 280CLD

Rev: 01 Date: 24 May 2021

Page 7 of 103

3. List of Abbreviations

% Percent

ΑE Adverse Event

ADE Adverse Device Effect

AGA American Gastroenterological Association

AR Authorized Representative

Body Mass Index BMI BUN Blood Urea Nitrogen

CSBM Complete Spontaneous Bowel Movement

Electronic Case Report Form **eCRF**

CI Confidence Interval

CIC Chronic Idiopathic Constipation

DSMB Data and Safety Monitoring Committee

EC **Ethics Committee ECG** Electrocardiogram **EDC** Electronic Data Capture

FA Full Analysis Set

FC **Functional Constipation** GCP **Good Clinical Practice**

FDA Food and Drug Administration

IBS-C Irritable Bowel Syndrome with Constipation

ICF Informed Consent Form

ICH International Conference on Harmonization of Technical Requirements for

Registration of Pharmaceuticals for Human Use

IFU Instruction for Use

Institutional Review Board **IRB ISF Investigator Site Files**

Intent To Treat ITT Milligram Mg Microgram mg minute(s) Min

Manufacturer MFR

NCAs National Competent Authorities

NSAIDs Non-Steroidal Anti-Inflammatory Drugs

mITT Modified Intent to Treat

OTC Over The Counter

PAC-QOL Patient Assessment of Constipation Quality of Life questionnaire

Doc No: 280CLD

Rev: 01 Date: 24 May 2021

Page 8 of 103

PEG Polyethylene glycol PI Principal Investigator

PP Per Protocol
QOL Quality of life

SAE Serious Adverse Event

SADE Serious Adverse Device Effect SBM Spontaneous Bowel Movement

US United States

USADE Unanticipated Serious Adverse Device Effect

Doc No: 280CLD

Rev: 01 Date: 24 May 2021

Page 9 of 103

4. Protocol Synopsis

Title	A Prospective, Randomized, Multi-center, Double-Blinded, Clinical Study		
	to Assess the Efficacy and Safety of Vibrant Capsule vs. Placebo, for the		
	Treatment of Chronic Idiopathic Constipation		
Indication	The Vibrant Capsule is intended for the treatment of adult subjects with		
	Chronic Idiopathic Constipation.		
Objectives	The objectives are to assess the efficacy and safety of Vibrant capsule		
	administered twice a week		
Number of	About 102 enrolled subjects including 10% drop-outs.		
Subjects			
Number of	The study will be performed in about 30 centers		
centers			
Study	Study duration is 10 to 12 weeks		
Duration	- 2 to 4weeks of run-in		
	- 8 weeks of treatment		
Design	The study is a prospective, randomized, multicenter, adaptive design, double		
	blinded clinical study, to evaluate the efficacy and safety of Vibrant Capsule		
	vs. placebo in relieving constipation in subjects with Chronic Idiopathic		
	Constipation.		
	Two arms will be assessed (at a ratio of 1:1 of Vibrant Treatment vs.		
	placebo): Vibrant Cancula administered twice a week (Monday and Thursday)		
	- Vibrant Capsule administered twice a week (Monday and Thursday)		
	- Placebo Capsule administered twice a week (Monday and Thursday)		
1			

Doc No: 280CLD

Rev: 01 Date: 24 May 2021

Page 10 of 103

This is a double-blind study. The subjects and the evaluators will be blinded to the treatment allocated to each subject. Each site will assign an unblinded person that will handle all issues related to capsule administration and accountability. The unblinded person will not be involved in any subject's assessments. Rest of the site staff will remain blind throughout the study.

An interim analysis will be performed after about 80 evaluable subjects will complete 8 weeks of treatment. The following parameters will be assessed: primary endpoint, and main safety parameters.

Depending on the results of the interim analyis:

- The study will be stopped,
- The study will continue as planned
- The sample size will be increased

Method

Subjects will come for 4 visits: Screening (visit 1), baseline (visit 2), after 4 treatment weeks from baseline (visit 3) and after 8 treatment weeks from baseline (Final visit, visit 4). A total of 8 treatment weeks.

Visit 1 - Screening: Subjects will be identified (by driving license or any other identity card) and consented into the study, PAC-QOL questionnaire will be completed. Following this visit, subjects who meet the study criteria will start a run-in period that will last 2-4 weeks. During this run in period subjects will be instructed to complete a simple seDiary every day before bed time. The eDiaryincludes questions on:

- Daily BM
- Change of subject's diet, if applicable (NOTE: the protocol will not ask/require the subjects to change anything in his/her diet)
- Change in sympotms as: brisol stool consistency, straining, bloating, and the other questions in the eDiary
- Medication

Doc No: 280CLD

Rev: 01 Date: 24 May 2021

Page 11 of 103

• Change in general health condition

Assessment of subject's eligibility will be based on 14 consecutive days of this eDiary. In accordance with nclusion #3, subjects with a weekly average of \geq 1 SBM and \leq 2.5 SBM will be eligible for the study (assuming all other criteria are met). In any case, subjects should have at least 1 SBM and not more than 3 SBMs during each of the run-in weeks.

Visit 2 - Baseline: After the run-in period, subjects will attend the Baseline visit and eligibility will be re-assessed. Subjects will be randomized with a ratio of 1:1 to either active capsule, or placebo capsule. for a treatment period of 8 weeks. Subjects will be trained on their treatment administration as well as on the usage of the base unit and will have their first capsule administration on site.

Subjects will be instructed to continue completion of the eDiary each day until the end of the study.

The first 2 weeks of treatment will be considered as a subjects' training period.

Visit 3 – after 4 weeks of treatment - an on site visit will take place to evaluate subject's treatment safety. Additional supply of capsules for additional 4 weeks of treatment will be dispensed to the subjects.

Visit 4 - Final visit –after another 4 weeks of treatment - an on site visit will take place to evaluate subject's treatment safety. Base units and remaining supplies (including capsules) will be collected.

Doc No: 280CLD

Rev: 01 Date: 24 May 2021

Page 12 of 103

PAC-QOLand Ease of use questionnaires will be completed.

During the entire study period, data reporting will be done on an electronic Case Report Form (eCRF) and an eDiary.

During the entire study period subjects will be asked to refrain from taking any medications or supplements to relieve their constipation.

Subjects will be authorized to use rescue medication after 3 consecutive days without a bowel movement.

Endpoints

Primary endpoints:

Efficacy Endpoints:

The two primary efficacy endpoints are the CSBM1 success rate, defined as an increase from the run-in period of at least one weekly Complete Spontaneous Bowel Movement (CSBM) during at least 6 of the 8 weeks of treatment, and CSBM2 success rate, defined as an increase from the run-in period of at least two weekly Complete Spontaneous Bowel Movement (CSBM) during at least 6 of the 8 weeks of treatment.

The study will be deemed successful if either the CSBM1 or the CSBM2 success rate is statistically significantly higher in the active arm than in the placebo arm.

NOTE:

• A spontaneous bowel movement (SBM) is defined as a bowel movement that occurs at least 48h after laxative/rescue intake and without digital maneuver.

Doc No: 280CLD

Rev: 01 Date: 24 May 2021

Page 13 of 103

• A complete spontaneous bowel movement (CSBM) is defined as a spontaneous bowel movement associated with a feeling of complete evacuation by the subject.

Safety Endpoints:

Safety endpoints include all adverse events related and unrelated to the study treatment

Secondary Efficacy Endpoints:

Secondary efficacy endpoints include:

- Change from baseline in average straining.
- CSBM1 expanded success rate, defined as an increase from the runin period of at least one weekly Complete Spontaneous Bowel Movement (CSBM) during at least 5 of the 8 weeks of treatment.
- Change from baseline in average stool consistency, using the Bristol Stool Scale
- CSBM2 expanded success rate, defined as an increase from the runin period of at least two weekly Complete Spontaneous Bowel Movement (CSBM) during at least 5 of the 8 weeks of treatment.
- Change from baseline in average bloating.

Additional Efficacy Endpoints:

Additional efficacy endpoints include:

- SBM success rate, defined as an increase from baseline period of at least one weekly Spontaneous Bowel Movement (SBM) during at least 6 of the 8 weeks of treatment.
- Incidence of Rescue Medication use during the treatment period

Doc No: 280CLD

Rev: 01 Date: 24 May 2021

Page 14 of 103

	 Change from baseline in weekly number of Spontaneous Bowel Movement (SBM). Change from baseline in weekly number of Complete Spontaneous Bowel Movement (CSBM). Rate of SBM ≤ 24 hours after first dose Change from baseline in average abdominal gas. Change from baseline in average abdominal pain. Change from baseline in abdominal discomfort. Time to occurrence of spontaneous bowel movement after first capsule activation. Change from baseline in quality of life using the PAC-QOL (Patient Assessment of Constipation Quality of Life) questionnaire. 			
Subject	Subjects with Chronic Idiopathic Constipation			
Population				
Inclusion	1. Subjects aged 22 years and older			
criteria	2. Subjects with Chronic Idiopathic Constipation (CIC) according to			
	Rome IV criteria			
	3. Subjects who have not experienced relief of their symptoms from one			
	or more available therapies (for at least one month at recommended			
	dose) or unable to tolerate these therapies			
	4. Subjects with an average of ≤2.5 Spontaneous Bowel Movements			
	(SBM) per week and ≥1 SBM per week (as a result of at least 1 SBM			
	and not more than 3 SBMs during each of the run-in weeks)			
	5. Subjects above 50 years old or <50 years old and with alarm signs			
	should have colonoscopy performed within 10 years prior to study			
	participation. Colonoscopy results should exclude GI obstruction			
	and/or GI malignancy			

Doc No: 280CLD

Rev: 01 Date: 24 May 2021

Page 15 of 103

	 Subject signed the Informed Consent Form (ICF) Female subjects must have a negative blood pregnancy test during screening, confirmed by a negative urine pregnancy test during baseline and must not be lactating prior to receiving study medication. For females of child-bearing potential, a hormonal (i.e., oral, implantable, or injectable) and single-barrier method, or a double-barrier method of birth control must be used throughout the study. All other female subjects must have the reason for their inability to bear children documented in the medical record [i.e., tubal ligation, hysterectomy, or post-menopausal (defined as a minimum of one year since the last menstrual period)]; in these circumstances, a pregnancy test will not be necessary.
Exclusion	History of complicated/obstructive diverticular disease
criteria	2. History of intestinal or colonic obstruction, or suspected intestinal
	obstruction.
	3. History of significant gastrointestinal disorder, including any form of
	inflammatory bowel disease or gastrointestinal malignancy (celiac
	disease is accepted if the subject has been treated and is in remission)
	4. Clinical evidence of current and significant gastroparesis
	5. Use of any of the following medications:
	Medications that may affect intestinal motility (including but
	not limited to prokinetics, anti-Parkinsonian medications,
	opiates, opioids, Verapamil, Nifedipine, iron, magnesium
	supplements, Tricyclic antidepressants (TCAs), Heparin,
	Warfarin and Baclofen.
	o With the exception of antidepressants (other than TCAs),
	thyroid or hormonal replacement therapy, when the subject has
	been on a stable dose for at least 3 months prior to enrollment.

Doc No: 280CLD

Rev: 01 Date: 24 May 2021

Page 16 of 103

6. Clinical evidence of significant respiratory, cardiovascular, renal, hepatic, biliary, endocrine, psychiatric or neurologic disease.

- 7. Presence of cardiac pacemaker, gastric electrical stimulator or any electrical implanted device.
- 8. History of, or current eating disorders, such as anorexia, bulimia, or compulsory overeating.
- 9. Diagnosis of mega-rectum or colon, congenital anorectal malformation, clinically significant rectocele, history of intestinal resection (with an exception for appendectomy, cholecystectomy and inguinal hernia repair), history of bariatric surgery or evidence of any structural abnormality of the gastrointestinal tract that might affect capsule's transit
- 10. History of Zenker's diverticulum, dysphagia, esophageal stricture, eosinophilic esophagitis or achalasia
- 11. Chronic use of non-steroidal anti-inflammatory drugs (NSAIDs): chronic use is defined as taking full dose NSAIDs more than three times a week for at least six months. Subjects on cardiac doses of aspirin may be enrolled in the study
- 12. Subjects with pelvic floor dysfunction/defecatory disorder, based on subject history
- 13. Participation in another interventional clinical study within one month prior to screening.
- 14. Women who are pregnant or lactating
- 15. Use of any medication for constipation relief during the study, except as rescue medication, as indicated by study rules
- 16. Inability to use an electronic daily Diary (on a computer, phone application, tablet or other electronic device) to report bowel movements, symptoms and medication usage

Doc No: 280CLD

Rev: 01 Date: 24 May 2021

Page 17 of 103

	17. Subject participated in a previous Vibrant study		
	18. Subjects planning to undergo MRI during the study		
	19. Any known allergy to soybean, beeswax, Calcium Carbonate, Gelatin,		
	Glycerin or Titanium dioxide		
	20. Any other condition which in the opinion of the investigator may		
	adversely affect the safety of the subject or would limit the subject's		
	ability to complete the study		
Statistical	Study Hypotheses:		
analysis	In this study, we will test the following hypotheses:		
•	$\bullet H_0: P_{al}-P_{sl}=0$		
	. H.D.D.40		
	$\bullet H_1: P_{a_1} - P_{s_1} \neq 0$		
	Where P _{a1} is the CSBM1 success rate in the selected active arm,		
	and P _{s1} , the CSBM1 success rate in the placebo arm.		
	AND:		
	• $H_0: P_{a2}-P_{s2}=0$		
	• $H_1: P_{a2}-P_{s2}\neq 0$		
	Where P _{a2} is the CSBM2 success rate in the selected active		
	arm, and P_{s2} , the CSBM2 success rate in the placebo arm.		
	arm, and 1 52, one Cobbine success rate in the practice arms		
	Sample size:		
	A sample size is calculated to test the null hypothesis. Calculations (using		
	SAS® proc power) show that a sample size of 92 subjects (46 in each of the		
	2 study arms), would provide 80% power at a study wise 5% level of		
	significance (two-sided), i.e. 2.5% for each one of the primary endpoints to		
	significance (two sided), i.e. 2.370 for each one of the primary endpoints to		

Doc No: 280CLD

Rev: 01 Date: 24 May 2021

Page 18 of 103

detect a difference of 28% in the success rate, assuming a success rate of 12% in the placebo arm.

The sample size will be increased to at least 102 subjects (54 in each of the 2 study arms) to account for a potential 10% of drop-out rate.

Main Efficacy Analysis:

The subject's CSBM1 success status (i.e. if the subjects achieve an increase from baseline of at least 1 weekly CSBM during at least 6 out of the 8 treatment weeks will be presented in tabular form by study arm, along with 95% Wilson score Confidence Intervals (CI) and will be compared between the study arms with a Cochran-Mantel-Haenszel test controlling for center.

The CSBM2 success rate will be analyzed in the same manner.

Doc No: 280CLD

Rev: 01 Date: 24 May 2021

Page 19 of 103

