15.7 Screening visit (day -28 to -14)

Subject will be identified by driving license or any other identity card. A copy of the identity card will be kept in the subject source documents.

Subjects will be asked to sign a consent form and will be screened for study eligibility according to inclusion and exclusion criteria. The daily bowel movements frequency, history of constipation, etiology of constipation and medication use (including prescription medication) will be thoroughly assessed. Subject demographic and medical information acquired from the subject or the subject's medical chart, including age, gender, previous medical history, concomitant medications, risk factors etc. will be also recorded on the eCRF.

For subjects over 50 years old a colonoscopy report should be confirmed and available during the screening visit (see incl. #5). The Bristol Stool Scale and Rome IV questionnaire (see Appendix A, B) will be completed and signed by the investigator, who is a physician to confirm the diagnosis of Chronic Idiopathic Constipation. Findings will be recorded on the eCRF.

In addition, subjects will undergo a physical examination including digital rectal examination, vital signs measurements and blood tests or blood test results from the past 3 months (providing no recently medical changes in patient illness). PAC-QOL (see Appendix D) be completed by the subject at screening visit.

The investigator will confirm their eligibility and their physical and mental suitability to participate in this study.

Eligible subjects will then be asked to refrain from taking any medication or supplement they are using to relieve their constipation during the entire study period except as allowed under the protocol (rescue treatment is allowed as per section 15.12).

Following the screening visit, subjects will enter the run-in period, in which an e-diary will be completed (on a daily basis and before bedtime) for 14 consecutive days (run-in period). During the screening visit, patient will be trained on how to complete a daily diary and on the definitions for "complete" evacuation and digital maneuver. On the day of screening, the coordinator should determine with the subject the last day of intake of constipation medication/aid and ensure that the last intake of constipation medication/aid has been taken more than 48 hours before the first diary entry.

Doc No: 280CLD		
Rev: 01	Date: 24 May 2021	
Page 50 of 103		

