During treatment period 1, Subjects will be instructed to adhere to rescue medications rules (section 15.12) and to continue filling a daily eDiary. This will include daily recordings of capsule intake, number and time of bowel movements, clinical symptoms score, AEs/change in their health condition, and medication/supplements usage, including rescue medication.

15.10 4 weeks visit (day 28 ± 2)

Four weeks after baseline visit, an on-site visit will be conducted to evaluate subject's treatment efficacy and safety.

During the visit, the following topics will be discussed to evaluate the following:

• subject's safety (including AE/ change in general health condition)

Page 53 of 103

- eDiary completion
- compliance with capsules intake
- change in concomitant medication/rescue administration
- evolution of constipation symptoms
- device accountability: at 4 weeks visit, subject must bring back to the site all remaining capsules (including spare capsule) in his/her possession and the capsules must be counted and accounted for.
- motivation of the subject, refreshing the definitions of what is "complete" evacuation and digital maneuver or any other relevant topic.

In this visit the subject will receive capsules supply for Treatment period 2 (period of 4 weeks between this visit and termination visit).

During treatment period 2, Subjects will be instructed to adhere to rescue medications rules (section 15.12) and to continue filling a daily eDiary. This will include daily recordings of capsule intake, number and time of bowel movements, clinical symptoms score, AEs/change in their health condition, and medication/supplements usage, including rescue medication

15.11 8 weeks visit / Termination (day 56 ± 2)

Eight weeks after baseline visit, an on-site visit (final visit) will be conducted to evaluate the following:

- subject's safety (including AE/ change in general health condition).
- eDiary completion
- concomitant medication/rescue administration
- evolution of constipation symptoms
- device accountability: At 8W visit, subject must bring back to the site the base unit and the router as well as all remaining capsules in his/her possession and the capsules must be counted and accounted for.
- PAC-QOL, and ease of use questionnaires

Page 54 of 103

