15.18 Study Schedule

Table 1 summarizes the required data collection from assessments and tests performed during the study.

Doc No: 280CLD

Rev: 01 Date: 24 May 2021

Page 57 of 103

Procedures	Screening	Baseline	4w visit	8w visit (Termination)
Visit No.	1	2	3	4
Day	-28 to -14	0	28 (±2 days)	56 (±2 days)
IC	+			
Eligibility Criteria	+	+		
Physical Exam	+			
Digital Rectal Exam	+			
Vital Signs	+			
Blood test (incl. pregnancy if applicable)	+			
Urine Pregnancy test (if applicable)		+		
On site administration of capsule		+		
Rome IV	+			
Bristol Stool	+			
PAC-QOL	+			+
Ease of use				+
Subject eDiary	+	+	+	+
Adverse Events		+	+	+
Device accountability			+	+
Concomitant Medication	+	+	+	+
Phone call	As needed	As needed	As needed	As needed

Table 1 – Study Schedule of Assessments

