17.9.8 Handling of Missing Data

Subjects with less than 6 weeks of diary data will be considered as failures for the CSBM and SBM success rates, as the primary imputation method for missing data.

Additional sensitivity analysis of the primary end-point will be performed to assess the impact of missing data on the study outcome using possible imputation methods for binary data:

- Multiple imputation for binary data.
- Observed Data: Use only subjects with 8 weeks of non-missing diary data and who did not withdraw early from study.
- Best Case Scenario: Assume all subjects with missing data in study group are successes; Assume all subjects in the placebo group with missing data are failures.
- Worst Case Scenario: Assume all subjects with missing data in study group are failures; Assume all subjects in the placebo group with missing data are successes.

In addition, for missing diary day, the number of bowel movement will be imputed to "0", and the intake of rescue medicine to "No". For the time to first SBM analysis, subjects with no known SBM will be considered left censored.

For the analyses of the other endpoints, no imputations for missing values will be performed.

Doc No: 280CLD

Rev: 01 Date: 24 May 2021

Page 75 of 103

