22. INFORMED CONSENT

Written informed consent must be obtained from each study subject. The subject will be asked to read the informed consent form and to sign the form to indicate consent to participate in the study.

The investigator will explain carefully to the subject the research nature of the study. The scope and aims of the research will be described together with known or foreseeable benefits, risks and discomforts that subjects may experience. Appropriate alternative treatments will be discussed so that the subject may determine whether or not he or she wishes to participate in the study. The subject must understand that throughout the study his or her participation remains voluntary and protected by the Declaration of Helsinki. The investigator is responsible for obtaining written (or witnessed) informed consent from potential subjects prior to study entry. The task of obtaining informed consent can be delegated, per PI discretion. Subjects will be given time to read the informed consent and ask any questions before being asked to sign the form. The informed consent (approved by the sponsor and the Ethics Committee) must be signed and dated by the subject and the investigator (or investigator's designee). One copy of the signed consent will be given to the subject, a second copy will be sent to the referral investigator and the original will be retained by the investigator. Subject should be identified during screening visit by driving license or any other identity card.

Subjects may withdraw their consent to participate in the study at any time without prejudice. The investigator may withdraw a subject if, in his clinical judgment, it is in the best interest of the subject or if the subject cannot comply with the protocol. Attempts should be made to complete any examinations and the sponsor must be notified of all withdrawals.

Should a protocol amendment be made, the subject's consent form may be revised to reflect the changes of the protocol. It is the responsibility of the investigator to ensure that an amended informed consent is approved or reviewed by the EC/IRB, and that it is signed by all subjects subsequently entered in the study and those currently in the study, if affected by the amendment.

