28. SUBJECT / STUDY DISCONTINUATION

Page 81 of 103

Subjects should be removed from the study whenever considered necessary for their welfare or when the subject expresses a desire to withdraw from the study. Non-compliance with the protocol, the occurrence of a Serious Adverse Event or any medical condition that, in the opinion of the investigator, warrants discontinuation from the study for the safety of the subject, may necessitate discontinuing a subject. If a subject is discontinued, the reason must be entered on the case report form and signed by the investigator. In case of any questionable situation, the study monitor or Vibrant Ltd. personnel should be consulted. When a subject is removed from the study as a result of Serious Adverse Event, a final physical examination must be performed. Subjects removed from the study because of an adverse event will be followed-up until the adverse event has been resolved.

In the case that the occurrence of adverse events is greater than anticipated, the clinical investigation will be suspended; in such a case, a safety committee will be arranged to decide if the study could be continued. The Ethics Committee will be notified and the results of the safety committee discussions will be brought for the EC/IRB review and decision.

Early termination could be a result of:

- 1. Withdrawal of informed consent by the subject.
- 2. Subjects who after inclusion develop medical diseases which may affect the function and interpretation of study results.
- 3. Serious protocol deviation.
- 4. Non-compliance with medical device administration or study procedures as determined by the sponsor.
- 5. Change in subject's condition.
- 6. Subject is Lost to follow-up.
- 7. Confirmed pregnancy.
- 8. Regulatory authorities stop the trial.

During the study, subjects exiting the trial will be replaced with new subjects, up to 10%

Site staff should set an early termination visit as soon as they become aware of subject's discontinuation. During this visit, any remaining study supplies should be collected and accountability should be conducted if applicable. 'End of study' from should be completed in source documents and any other relevant information should be documented (for example, in case of AE).

Doc No: 280CLD

Rev: 01 Date: 24 May 2021

Page 82 of 103

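### PAC-QOL is scheduled after baseline only at week 8 and is not named at the early-termination visit, so its table will in effect describe completers

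*Combined protocol and SAP*

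**What the plan says.** **Collection.** Section 15.7 has "PAC-QOL (see Appendix D) be completed by the subject at screening visit". After treatment starts, the synopsis places it at visit 4: "PAC-QOLand Ease of use questionnaires will be completed". Section 15.11, which describes the visit eight weeks after baseline, lists "PAC-QOL, and ease of use questionnaires". Table 1 marks PAC-QOL at screening and in the column headed "8w visit (Termination", whose day is 56 ± 2. Neither the baseline visit nor the 4-week visit carries a mark.

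**Early exit.** Section 28 calls for an early-termination visit and says: "During this visit, any remaining study supplies should be collected and accountability should be conducted if applicable". It adds an end-of-study form, and "any other relevant information should be documented (for example, in case of AE" is its open-ended item. Section 22 says of withdrawals in general: "Attempts should be made to complete any examinations and the sponsor must be notified of all withdrawals". Neither section names PAC-QOL.

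**Analysis.** Change in PAC-QOL is the last of the additional efficacy endpoints in 17.2.3. Section 17.9.5 says that it will be tabulated and does not name it in the ANCOVA list. Section 17.9.8 states: "For the analyses of the other endpoints, no imputations for missing values will be performed". Under 17.8.2 (ITT) and 17.8.3 (mITT), a subject with no valid post-baseline assessment is left out of the analysis concerned.

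**The concern.** Each rule is ordinary on its own; the difficulty comes from the combination. A subject who stops before week 8 has no scheduled post-treatment PAC-QOL, receives no imputed value and leaves the table. Those who stop may well include subjects without benefit or with side effects. If so, the remaining subjects make the improvement within each arm look better than it was for everyone randomised, and unequal drop-out could distort the contrast between arms.

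The other change-from-baseline endpoints are less exposed. Symptoms and bowel movements are recorded daily in the eDiary, so a subject who leaves at week 5 has already supplied post-baseline data. PAC-QOL has no such backup, and a questionnaire that is not completed at exit generally cannot be recovered later.

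**Working it through.** **1. The plan's own figure.** Section 17.4 gives 46 per arm for 12% against 40% (12% + 28%), two-sided 2.5%, 80% power. With the pooled-variance formula:

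n = [z(0.9875)·√(2·0.26·0.74) + z(0.80)·√(0.12·0.88 + 0.40·0.60)]² / 0.28²

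= [2.2414·0.6203 + 0.8416·0.5879]² / 0.0784 = 3.554 / 0.0784 = 45.3, so 46 per arm and 92 in total. Power at 46 per arm is 80.7%. Adding 10%: 92 × 1.10 = 101.2, rounded up to 102. The figure reproduces, and nothing below changes it.

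**2. What a subject who leaves before day 54 supplies, by visit.**

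| Visit | PAC-QOL named? | Source |
|---|---|---|
| Screening | yes | 15.7, Table 1 |
| Baseline | no | Table 1 |
| Week 4 | no | 15.10, Table 1 |
| Early termination | no | section 28 |
| Week 8, day 56 ± 2 | yes, but not reached | synopsis, 15.11, Table 1 |

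The result is a pre-treatment score and no scheduled post-treatment score.

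**3. Number affected.** Missing = N × d, where d is the drop-out proportion.

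- Planned: 102 × 0.10 = 10.2, so about 10 missing and about 92 in the table.
- Assumed range: d = 5% leaves 102 × 0.95 = 96.9, about 97; d = 20% leaves 102 × 0.80 = 81.6, about 82.
- At the 250 maximum in 17.5.3: 250 × 0.10 = 25 missing.

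**4. Bias.** The documents give no PAC-QOL standard deviation, effect size or drop-out by arm, so this step is illustration only. Let g be the amount by which drop-outs would score worse than completers in the same arm. Within an arm, completers look better than all randomised by d·g. Between arms, the bias is d_A·g_A − d_P·g_P (A active, P placebo; positive favours active). Assume the same g in both arms, from 0.25 to 1.0 SD:

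- 10% in each arm: (0.10 − 0.10)·g = 0.
- 15% active, 5% placebo: 0.10·g = 0.025 to 0.10 SD in favour of active.
- 5% active, 15% placebo: −0.10·g = 0.025 to 0.10 SD against active.

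The within-arm overstatement remains in all three cases. The between-arm bias may be zero or have either sign.

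**The case against.** **No rule excludes drop-outs as such.** A reader might infer that every drop-out is barred from this endpoint. The documents do not say so. The analysis-set rule removes only subjects without a valid post-baseline assessment. Section 22 asks for attempts to complete examinations, section 28 leaves room for other relevant information, and the week-8 visit also bears the label Termination. A subject who happened to fill in PAC-QOL on leaving could have a usable score. This part of the objection stands, and it is why the point says most drop-outs and not all. It does not remove the gap. The Termination label is tied to day 56 ± 2, early exit has its own visit and its own list, and the line on examinations names no questionnaire. About 30 centres would each have to infer the requirement.

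**The endpoint has low standing.** PAC-QOL lies outside the hierarchy of 17.9.2.3, and no test or model is assigned specifically to it. That is correct and limits the consequence. The general rule for comparing means in 17.9.1 could still be applied, and a table by arm will be read as a comparison.

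**The treatment effect is not shown to be exaggerated.** A reader might infer that completers' results necessarily flatter the active arm. Take assumed mean changes of −0.8 (active) and −0.5 (placebo) in completers and 0 in drop-outs. The completers' difference is −0.30. With 15% active and 5% placebo drop-out, the all-subject difference is 0.85·(−0.8) − 0.95·(−0.5) = −0.205. With the rates reversed, it is 0.95·(−0.8) − 0.85·(−0.5) = −0.335. The same inputs overstate the effect in one case and understate it in the other, so no percentage of inflation can be attached to the plan.

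**Replacement.** Section 28 lets exiting subjects be replaced, up to 10%. This restores numbers but not the outcomes of those who left.

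**Conclusion.** The point holds as a minor, cheaply repaired gap in data collection. Followed as written, the plan yields no PAC-QOL outcome for most subjects who leave early, and the table will in effect describe completers. The count of about 10 in 102 rests on the plan's 10% drop-out and on few sites collecting the questionnaire at exit unprompted. The view that improvement within arms is overstated rests on the assumption that leavers fare worse than completers, which is plausible but not documented. No claim is made about the size or direction of bias between arms. The study's success criterion and error control are untouched.

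**What to change.** 1. In section 28, name PAC-QOL among the procedures of the early-termination visit.
2. In Table 1, add an early-termination column with PAC-QOL marked.
3. In 17.9.5, keep the week-8 PAC-QOL table as planned and add a supportive table that includes the exit values with the study day on which each was taken. The exit score should not stand in for the week-8 score: that would be a last-observation approach, mixing shorter and full treatment, and would need reconciling with the no-imputation rule. Showing observed exit values separately leaves 17.9.8 as it is.

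The cost is one self-completed questionnaire at a visit that the plan already requires, and a few lines of text.

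The gain is partial. Exit scores will come from shorter treatment, some of them possibly from the two-week training period. Subjects who withdraw consent or are lost to follow-up may not attend. Subjects with less than two weeks of valid diary remain non-evaluable in the mITT set, the main efficacy set under 17.8.5; the ITT set has no such diary minimum, so their exit values could be shown there.
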